## 4.11.2 Laboratory Data

Clinical laboratory parameters (including chemistry, hematology (including RBC indices and WBC count with differentials), coagulation and urinalysis) will be listed and abnormal parameters will be flagged as high (H) or low (L) according to reference ranges. Absolute (observed) values and changes from baseline (continuous variables) will be summarized for each parameter and scheduled time point by cohort and period. The last lab value will be used for summary analysis if repeated measurements are made at any time point.

For summary statistics, a lab value with "<" will be replaced with a numeric value by removing the "<" sign. In the listings, the values will be displayed as originally reported by the laboratory.

Laboratory parameter values will be graded according to the Common Terminology Criteria for Adverse Events (CTCAE). Shift tables by cohort and by period will be produced for laboratory parameters graded by CTCAE. These tables will summarize the number of subjects with each baseline grade relative to the normal ranges and changes to the worst highest grade assessed post-dose during the period.

Laboratory parameters planned in the study are outlined in Table 10 of the protocol. Any additional parameters collected as part of investigations will be listed only. Laboratory parameters will be presented in SI units, BUN will be converted to SI unit ( mmol/L).

## 4.11.3 Electrocardiograms

ECG parameters will be measured at the specified time points and will include heart rate, PR, RR, QRS, QT, and corrected QT interval corrected using Fridericia's formula ( $QTcF = QT/RR^{1/3}$ ). The variables will be listed individually.

Three or more replicate measurements are taken at each protocol time point and the arithmetic mean of the evaluable/available measurements will be taken as the measurement to be used for summary statistics. Arithmetic mean values will also be included into the listings.

For ECG variables, the change from baseline will be derived using the arithmetic mean value of each time-point triplicate minus the arithmetic mean of baseline triplicate values.

Absolute (observed) values and changes from baseline in the ECG variables will be summarized by cohort, period and time point.

An outlier analysis will be performed that will summarize the frequency and percentage of subjects who meet any of the following outlier criteria at each visit by cohort and period:

- QT, QTcF interval > 450 msec to ≤ 480 msec
- QT, QTcF interval > 480 msec to ≤ 500 msec
- QT, QTcF interval > 500 msec
- QT, QTcF interval increases from baseline > 30 msec to ≤ 60 msec
- QT, QTcF interval increases from baseline > 60 msec

#### *4.11.4 Vital Signs*

Vital signs data (systolic and diastolic blood pressure, heart rate, temperature and respiration rate) will be listed for individual subjects. Summary statistics of absolute (observed) values and changes from baseline will be calculated for each parameter and scheduled time point by cohort and dosing regimen.

#### *4.11.5 Physical Examination*

Physical examination data will be listed individually over time.

### **4.12 Pharmacokinetic Data Analysis Plan**

All plasma concentration data will be listed for each individual subject and summarized at each time point by cohort and period. Individual and mean concentrations versus nominal time on linear and semi-log scales will be presented graphically by period.

The PK population will be used to present the summary of PK parameters.

#### *4.12.1 Values Below the Limit of Quantification and Missing Values*

If a Below the Limit of Quantification (BLQ) value occurs in a profile before the first measurable concentration, it will be assigned a value of zero concentration. If a BLQ value occurs after a measurable concentration in a profile and is followed by a value above the lower limit of quantification, then the BLQ value will be omitted following visual inspection of the plasma concentration versus time profile to assess the appropriateness of this assignment. If a BLQ value occurs at the end of a collection profile (after the last quantifiable concentration), the value will be treated as missing data. If 2 BLQ values occur in succession, the profile will be deemed to have terminated at the first BLQ value and any subsequent concentrations will be omitted from PK calculations following visual inspection of the plasma concentration versus time profile to assess the appropriateness of this assignment.

Samples with no reportable value due to a bioanalytical issue or missing samples will be set to missing, and will not be included in the PK calculations. If a subject vomited following dose administration, then their profile will be examined to determine the impact of this on PK parameter estimation.

When calculating the mean or median value for a concentration at a given time point, all BLQ values will be set to zero except when an individual BLQ falls between 2 quantifiable values, in which case it will be omitted.

For tabulation, graphical representation, and calculation purposes, all samples with no reportable value (or missing samples) observed after dosing will be set to missing.

#### *4.12.2 Pharmacokinetic Parameters*

Individual plasma concentration data for ALXN1840, assessed as plasma total Mo concentration-time data, with actual sampling dates and times calculated relative to the actual date and time for the start of dose administration in each Dosing Period, will be used to derive the PK parameters. PK parameters will be calculated

using non-compartmental analyses with Phoenix® WinNonlin® Version 8.0 or higher. If missing actual sampling dates and times, then the nominal time relative to the start time of the administration will be used.

The following plasma total Mo PK parameters will be derived for each subject and period:

- **Cmax [ng/mL]:** Maximum observed plasma concentration
  - o For multiple peaks, the highest post-dose concentration will be reported as Cmax
- **Cmax\_n[ng/mL]/[mg]:** Dose normalized maximum observed plasma concentration
  - o Calculated as Cmax /dose
- **Tmax [h]:** Time to maximum observed plasma concentration
  - o In case that multiple peaks are available of equal magnitude at the highest post-dose concentration, the earliest Tmax will be reported
- **AUCt [h\* ng/mL]:** Area under the plasma concentration versus time curve from time zero (dosing) to the last quantifiable concentration
- **AUCt\_n [h\* ng/mL]/[mg]:** Dose normalized area under the plasma concentration versus time curve from time zero (dosing) to the last quantifiable concentration
  - o Calculated as AUCt /dose
- **AUC∞ [h\* ng/mL]:** Area under the plasma concentration versus time curve from time zero (dosing) extrapolated to infinity
- **AUCextr (%):** The percentage of AUC∞ extrapolated.
  - o Subjects with an AUCextrap > 20% will be flagged, and parameters that are dependent on AUC∞ will also be flagged (AUC∞, **AUC∞\_n**, CL/F, Vd/F and Frel).
- **AUC∞\_n [h\* ng/mL]/[mg]:** dose normalized area under the plasma concentration versus time curve from time zero (dosing) extrapolated to infinity
  - o Calculated as AUC∞ /dose
- **λz [1/h]:** Apparent terminal-phase elimination rate constant
  - o Only those data points that are judged to describe the terminal log-linear decline will be used in the regression
  - o A minimum number of 3 data points in the terminal phase will be used in calculating λz, with the line of regression starting at any post-Cmax data point (Cmax should not be part of the regression slope)
- **t1/2 [h]:** Terminal elimination half-life
  - o Calculated as ln(2)/ λz
- **CL/F [L/h]:** Apparent total clearance

- Calculated as  $\text{dose}/\text{AUC}_{\infty}$
- **$V_d/F$  [L]:** Apparent volume of distribution during terminal phase
  - Calculated as  $\text{dose}/(\lambda_z * \text{AUC}_{\infty})$
- **$F_{\text{rel}}$ :** Relative bioavailability defined as the ratio of the geometric means for the dose normalized  $\text{AUC}_{\infty}$  parameter for the ALXN1840 Japanese cohort over the ALXN1840 non-Japanese cohort by dose strength of 15 mg or 60 mg.

PK parameters will be listed for each individual subject and summarized by cohort and period. Descriptive statistics for PK parameters will include number of observations (n), arithmetic mean (Mean), standard deviation (SD), arithmetic coefficient of variation (%CV), geometric mean, geometric %CV, median, minimum and maximum.

For the relative bioavailability, a 95% CI for the ratio of the geometric means will be provided. To calculate CIs of geometric mean ratios, dose normalized  $\text{AUC}_{\infty}$  will be log-transformed and CIs will be constructed for the mean difference of log-transformed parameters, assuming that log-transformed parameters are normally distributed. The CIs are then back-transformed to receive CIs for the geometric mean ratios. The geometric mean ratios and their 95% CIs will be tabulated.

Some PK parameters may not be calculated for all or some subjects if the concentration data are not deemed to be amenable to evaluation. Explanations for PK parameters that could not be estimated will be provided in the CSR. Subjects who vomit post-dose will have their plasma concentration profile evaluated for inclusion in the PK analysis.

Analyses of other PK data including, but not limited to those, of PUF Mo may be conducted.

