Abbreviations: AE = adverse event; BP = blood pressure; Cp = ceruloplasmin; CpC = ceruloplasmin-bound copper; CRU = Clinical Research Unit; Cu = copper; EOS or ET = End of Study or Early Termination; FSH = follicle stimulating hormone; HIV = human immunodeficiency virus; Mo = molybdenum; NCC = non-ceruloplasmin-bound copper; PD = pharmacodynamic(s); PK = pharmacokinetics; PR = pulse rate; RR = respiratory rate; T = temperature.

f Triplicate 12-lead ECG will be taken pre-dose, at 4 hrs post-dose (before lunch) on Day 1 (see Table 2), Day 2, and at EOS for both Dosing Periods. ECGs will be conducted before PK/PD/biomarker blood sampling if these 2 events occur at the same time.

<sup>g At screening, supine and standing (orthostatic) blood pressures will be measured to exclude volunteers who are prone to orthostatic hypotension.

<sup>h Only chemistry sample and non-fasting safety blood samples will be obtained on Day 10.

<sup>1 Serum pregnancy test is not required once the subject is confirmed to be post-menopausal.

<sup>j Blood samples for the measurement of plasma total Mo (PK) and total Cu, Cp, CpC, and NCC (PD)

<sup>k See Table 2 for details

Schedule of Assessments During CRU Confinement For Each Dosing Period Table 2:

Study Day	Time (hour)	PK/PD/Biomarker samples	Vital Signs	Hematology, Chemistry, Urinalysis, and Coagulation	ECG b
	-2				
	-1				
	-0.5	X	Х		Х
	0 a				
D1	1	X	X		
	2	X			
	3	X			
	4	X	Х	X	Xc
	5	X			
	6	X			
	8	X	Х		
	12	X	Х		
D2	24	X	Х	X	Х
D3	48	X			
D4	72	X			
D5	96	X		X	
D6	120	X			
D7	144	X			
D8	168	X			
D9	192	X			
D10	216	X		X d	
D11	240	X			

Abbreviations: CRU = Clinical Research Unit; D = day; PD = pharmacodynamic(s); PK = pharmacokinetic(s).

<sup>a Hour 0 corresponds to the time of ALXN1840 administration. Unless stated otherwise, times listed are in relation to ALXN1840 dosing.

b ECG will be conducted before PK/PD/biomarker blood sampling if these 2 events occur at the same time.

c 12-lead ECG will be performed 4 hours post-dose (before lunch).

d Only chemistry sample and non-fasting safety blood samples will be obtained on Day 10

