# 2.2. Background

ALXN1840 (bis-choline tetrathiomolybdate) is a novel, first-in-class, copper (Cu)-protein binding agent in development for the treatment of WD. ALXN1840 is targeted to address the following unmet medical needs:

- Rapid and sustained control of Cu and clinical symptoms of WD, through the rapid formation of virtually irreversible Cu-tetrathiomolybdate-albumin tripartite complexes, without mobilizing free Cu that could potentially cause tissue toxicity including acute neurological deterioration. This hypothesis is supported by results from Study WTX101-201 in patients with WD (Weiss, 2017).
- Improved compliance over current chelator therapy through improved tolerability and the convenience of a simplified dosing regimen (once daily) compared to current therapeutic options (multiple daily dosing).

ALXN1840 has been selected for development in WD due to its improved stability properties over ammonium tetrathiomolybdate, which has previously been studied in WD and other indications. The salt cation (ammonium or bis-choline) does not impact the PK or pharmacodynamic (PD) effects of tetrathiomolybdate. Ammonium tetrathiomolybdate as well as bis-choline tetrathiomolybdate non-clinical and clinical data reported to date support the efficacy and safety of ALXN1840.

Two Phase 1 healthy subject studies (WTX101-101 and WTX101-102, N=18 for each study) to assess the PK of ALXN1840 have been completed. Total plasma molybdenum (Mo) concentrations were used as a surrogate PK measure for tetrathiomolybdate.

Study WTX101-101 evaluated the relative exposure of 60 mg ALXN1840 ( $2 \times 30$  mg uncoated capsules [UCs]) without and with co-administration of a long-acting proton pump inhibitor (PPI) under fasted conditions, the latter also under fed conditions. Based on total plasma Mo, administration of the UC + PPI under fasted conditions resulted in a 30% increase in exposure compared to the UC alone. Administration of the UC + PPI fed resulted in a 22% decrease in exposure compared to the UC + PPI fasted. There was a decrease in the between-subject

variability when the UC was administered with a PPI. The mean terminal elimination half-life  $(t_{1/2})$  for total Mo was similar for all 3 treatments, with an overall mean of ~51 hours or slightly over 2 days (Table 3).

Table 3: Total Molybdenum Pharmacokinetic Parameters from Study WTX101-101

Parameter a	Treatment			
rarameter	UC Fasted	UC + PPI Fasted	UC + PPI Fed	

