## **4. STATISTICAL ANALYSES**

In general, descriptive statistics for continuous variables will include number of non-missing values (n), arithmetic mean (Mean), standard deviation (SD), median, minimum, and maximum.

Descriptive statistics for PK parameters will include number of observations (n), arithmetic mean (Mean), standard deviation (SD), arithmetic coefficient of variation (%CV), geometric mean, geometric %CV, median, minimum and maximum.

Categorical variables will be summarized using frequency counts and percentages.

For all tables, except PK parameter tables, descriptive statistics for minimum and maximum will be presented with the same decimal digits as the original data, and with 1 more decimal place than the original data for mean and median; SD will be reported with 2 more decimal places than the original data.

PK parameters will be presented as follows in the listing:  $C_{max}$  and  $T_{max}$  will be presented as given in the raw data;  $AUC_t$ ,  $AUC_{\infty}$ ,  $\lambda_z$ ,  $t_{1/2}$ , CL or CL/F, and  $V_d$  or  $V_d/F$  will be presented with 3 decimal places. Special characters (including subscripts) will not be presented in the tables, listings or figures. Descriptive statistics for PK parameters will be presented with decimal places as appropriate for the particular parameter and cohort.

The analyses will be presented by cohort and period. All collected data will be presented in by-subject listings. Listings will be ordered by cohort, period and subject number and will include all randomized subjects. Deviations from this scheme, if any, will be specified in the relevant section.

Baseline will be defined as the last non-missing value among assessments recorded prior to administration of study drug within respective period. Changes from baseline values will be calculated by period as the post-baseline assessment value minus the baseline value. Only observed values from scheduled time points will be used to create summary tables.

Early Termination (ET) visits will be recoded to ET visits where necessary and reported as ET.

Deviations from the planned analyses will be described in the final clinical study report (CSR).

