#### 4.13.3 Pharmacodynamic and Biomarker Analyses

Individual ALXN1840 PD and biomarkers, assessed as plasma total Cu (PD), NCC (PD),  $NCC_{corrected}$  (PD), Cp (biomarker), and CpC (biomarker) concentration-time data (including measured, absolute and percent changes from baseline) will be listed and summarized at each time point by cohort and period with descriptive statistics. The NCC level will be corrected for the amount of Cu bound to the TPC ( $NCC_{corrected}$ ).

Individual subject data (and change from baseline) of plasma Cp and copper levels (total Cu, Cp, CpC and NCC) will be presented graphically for each cohort and period. Mean plots (for measured and change from baseline value) of cohort and dose will be overlaid (separately for PD and biomarker parameters) and presented over time.

Analyses of other biomarker data including, but not limited to, those of PUF Cu may be conducted.

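### SAP 4.12.2 derives AUC and the terminal slope from uncorrected total molybdenum and has no rule for a quantifiable pre-dose value; any background would inflate 15 mg exposure about four times more, in relative terms, than 60 mg

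*SAP*

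**What the plan says.** - **Analyte.** Protocol 2.2 says of the two completed healthy-subject studies: "Total plasma molybdenum (Mo) concentrations were used as a surrogate PK measure for tetrathiomolybdate". SAP 4.12.2 keeps that measure, working from "Individual plasma concentration data for ALXN1840, assessed as plasma total Mo concentration-time data". AUCt is the "Area under the plasma concentration versus time curve from time zero (dosing) to the last quantifiable concentration". No parameter definition in that section subtracts anything.
- **Pre-dose sample.** Protocol Table 2 marks a PK/PD/biomarker sample at -0.5 h, and it applies to each dosing period. Footnote j of Table 1 says these samples measure total Mo.
- **Early values.** SAP 4.12.1 covers them only when they are below the limit of quantification. For a BLQ value ahead of the first measurable one, "it will be assigned a value of zero concentration". A quantifiable pre-dose value has no rule.
- **Baseline.** SAP section 4 has a general definition: "Baseline will be defined as the last non-missing value among assessments recorded prior to administration of study drug within respective period". Among the plasma analytes, only the PD and biomarker measures use it. SAP 4.13.3 says of them: "concentration-time data (including measured, absolute and percent changes from baseline) will be listed and summarized at each time point by cohort and period".
- **Deferral.** Protocol 9.4.3.1 leaves PK detail to a PK/PD data analysis plan. SAP 4.12 carries the title of a pharmacokinetic data analysis plan and contains no correction.

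**The concern.** An elemental assay cannot tell drug-derived molybdenum from any other. If a subject has a quantifiable concentration before the first dose, that amount stays in every later sample. A constant background adds the same area at both doses, so it is a larger share of the smaller 15 mg AUC. Because it does not decay, it also flattens the terminal slope, which lengthens the apparent half-life and enlarges the extrapolated part of AUC∞.

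Exact proportionality would then look like a less-than-proportional rise. At 15 mg, AUC and half-life would read high and CL/F low, and the by-dose Frel would be pulled toward 1. The scheduled sample that could show and remove this is not used for the purpose.

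**Working it through.** **Inputs from the documents**
- Protocol Table 4, EC tablet fasted, 60 mg: AUC(0-t) 16,026 h·ng/mL, Cmax 376 ng/mL, t½ 51.0 h.
- Sampling runs to 240 h (Protocol Table 2). Doses are 15 mg and 60 mg.

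**Assumptions**
- Constant background b of 0.25 to 2 ng/mL, equal in both periods. The documents give neither a level nor an LLOQ.
- Dose proportionality, so the 15 mg AUCt is 16,026 / 4 = 4,006.5 h·ng/mL.

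**The plan's own precision, as a yardstick.** The half-width in SAP 3.3 reproduces: t(0.95, 18 df) × 0.35 × √(2/10) = 0.2714, and exp(±0.2714) = 0.762 to 1.312, against the stated 0.271 and 0.76 to 1.31.

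**AUCt.** A quantifiable background keeps every sample quantifiable, so AUCt runs to 240 h and the added area is 240 × b at either dose. At b = 1 this is 240 / 4,006.5 = 6.0% at 15 mg and 240 / 16,026 = 1.5% at 60 mg. The factor of four is the dose ratio.

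**AUC∞ and half-life.** These come from a non-compartmental calculation on a one-compartment profile (t½ 51 h, scheduled times, scaled to AUCt 16,026), with λz from the last 5 or the last 3 points. Ranges run between those two choices.

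| b (ng/mL) | AUCt 15 mg | AUCt 60 mg | AUC∞ 15 mg | AUC∞ 60 mg | t½ 15 mg (true 51 h) | Dose-normalised AUC∞ ratio 60/15 |
|---|---|---|---|---|---|---|
| 0.25 | +1.5% | +0.4% | +2.2% | +0.5 to 0.6% | 54–55 h | 0.98 |
| 0.5 | +3.0% | +0.7% | +4.4 to 4.6% | +1.1% | 57–59 h | 0.97 |
| 1 | +6.0% | +1.5% | +8.9 to 9.4% | +2.2% | 63–68 h | 0.93–0.94 |
| 2 | +12.0% | +3.0% | +18.6 to 19.9% | +4.4 to 4.6% | 75–84 h | 0.87–0.88 |

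The last column is (1 + 60 mg inflation) / (1 + 15 mg inflation); for b = 2 with 3 points, 1.0455 / 1.199 = 0.87. The relative inflation of AUC∞ is 4.0 to 4.4 times larger at 15 mg.

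**Power model.** On AUCt before dose-normalisation, the slope is ln[(16,026 + 240b) / (4,006.5 + 240b)] / ln 4. It is 0.992 at b = 0.25, 0.969 at b = 1 and 0.940 at b = 2, when the truth is 1.

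**CL/F at 15 mg.** This is dose / AUC∞, so at b = 2 it reads 1 / 1.199 = 0.83 of its true value.

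**Cmax.** At b = 2, 2 / (376 / 4) = 2.1% at 15 mg.

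**Cohort ratio, equal background.** A true AUCt ratio of 1.25 (illustrative) at b = 1 reads (1.25 × 4,006.5 + 240) / (4,006.5 + 240) = 1.236 at 15 mg, and 1.246 at 60 mg by the same formula.

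**Cohort ratio, background of 1 ng/mL in one cohort only.** The pooled AUC∞ ratio shifts by √(1.089 × 1.0215) = 1.055 to √(1.0938 × 1.0224) = 1.058, about 5 to 6%.

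**Sensitivity to profile shape.** The one-compartment profile peaks at 211 ng/mL, below the 376 in Table 4. A bi-exponential profile scaled to AUC∞ of about 17,300, with λz from the last 4 points, gives 15 mg AUC∞ inflation of 4.3, 8.9 and 19.0% at b = 0.5, 1 and 2, so the result does not hinge on the shape. Ending that profile at 192 h instead of 240 h reduces the b = 1 figures from 8.9% to 7.4% and from about 68 h to 58 h.

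**The case against.** **No background is shown to exist.** This stands. The only in-document comparison gives no support: in Protocol Table 4 the fed EC arm has much lower exposure than the fasted arm (AUC∞ 6,973 against 17,258), yet its mean half-life is shorter (43.5 h against 51.0 h), where a background should lengthen it. That evidence is weak, with n = 15, SD 20.9 h and no statement on whether that study corrected for baseline.

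**The primary objective is little touched.** This stands too. A reader might infer a biased primary cohort comparison at 15 mg. There is no such stand-alone test: the ANOVA in SAP 4.12.3 pools both periods, and the by-dose cohort results are Frel and descriptive summaries. An equal background barely moves the cohort ratio. No passage supports a difference in background between cohorts, and meals are standard during confinement (Protocol 5.3.1). Even the one-sided case above is small beside a planned interval of 0.76 to 1.31.

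**Dose proportionality is exploratory.** It has no acceptance limits, so a ratio of 0.94 triggers no decision. Nor is a true factor of four certain, since Protocol 2.2 reports no clear proportionality in Study WTX101-201.

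**Safeguards exist.** SAP 4.12 already summarises concentrations at each time point by cohort and period, so a background would be visible and no further summary is needed. SAP 4.12.2 limits λz to points judged log-linear and flags extrapolation above 20%. On the mean profile that flag would not fire: at b = 2 the extrapolated share at 15 mg is 9.3 to 10.3%. Seeing a background is also not the same as having a rule for it.

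**Carry-over.** A reader might add Period 1 residue to the complaint. At 14 days (336 h) the share of the 15 mg dose remaining is 2^(-336/51) = 1.0%, or 0.8% with a 48 h half-life. That is negligible against a 60 mg dose, and the correction proposed here would not remove it.

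**Conclusion.** The gap is real: the SAP computes AUCt, AUC∞, λz and what follows from them on uncorrected total Mo, and has no rule for a quantifiable pre-dose value. Whether it matters depends on a background level that the documents do not give.

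The figures in the table rest on a constant background of 0.25 to 2 ng/mL, equal in both periods, and on dose proportionality. Under those assumptions the bias at 15 mg ranges from minor to enough to be read as less-than-proportional exposure. It bears on the exploratory dose-proportionality analysis and the 15 mg AUC, half-life, CL/F and Frel. It is not a demonstrated bias in the primary cohort comparison, and Cmax needs no correction. This is an inexpensive improvement to the plan rather than a flaw that undermines the study.

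**What to change.** Add to SAP 4.12.2: if any Period 1 pre-dose total Mo value is quantifiable, AUCt, AUC∞, λz and the parameters derived from them are also derived after subtracting each subject's Period 1 pre-dose concentration (zero if BLQ) from all samples of both periods. Corrected values at or below zero are treated as BLQ. The ANOVA, Frel and dose-proportionality analyses are repeated on these values as a sensitivity analysis, reported beside the uncorrected results.

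The Period 1 value is the one to use because prior exposure to ALXN1840 is an exclusion criterion (Protocol 5.2), so it contains no study drug; the Period 2 value may contain a trace.

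The cost is one further non-compartmental run on samples already scheduled. The downside is that one pre-dose value per subject carries assay noise into every corrected concentration, most of all in the late 15 mg samples, which is why the uncorrected analysis should stay. If all Period 1 pre-dose values are BLQ, nothing changes; by the same token, the rule cannot address a background below the assay limit.

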Abbreviations:  $AUC_{\infty}$  = area under the plasma concentration versus time curve with the last concentration extrapolated based on the  $\lambda_z$ ;  $AUC_{(0-t)}$  = area under the plasma concentration versus time curve to the last measurable concentration; CL/F = clearance/bioavailability;  $C_{max}$  = maximum observed concentration; EC = enteric-coated;  $\lambda_z$  = elimination rate constant; PPI = proton pump inhibitor;  $t_{1/2}$  = terminal elimination half-life;  $T_{lag}$  = lag time;  $t_{max}$  = time to maximum concentration; UC = uncoated capsule; Vz/F = apparent volume of distribution.

A total of 18 subjects were enrolled, completed the study, and were included in the safety analysis. There were no deaths, SAEs, or discontinuation due to AEs in this study. Overall, a total of 21 AEs were reported by 7 (39%) subjects in this study. The percentages of subjects reporting AEs following ALXN1840 dosing were similar following each of the 3 study treatments. All AEs reported in the study were mild (Grade 1) in severity. Diarrhea, headache, and nasal congestion were the most frequently reported AEs in this study and were each reported by 2 (11%) subjects. There was 1 AE considered by the Investigator to be probably related to study drug (nausea) and 5 AEs considered to be possibly related to study drug (4 events of diarrhea and 1 event of nausea); all other AEs were considered to be unrelated to the study drugs. There were no clinically important trends in the laboratory, vital sign, ECG, or physical examination assessments in this study.

There were no apparent relationships between clearance/bioavailability (CL/F) and body size (weight, body mass index [BMI]) in either Study WTX101-101 or Study WTX101-102,

b Parameter could not be estimated for any subject for this treatment.

suggesting that a fixed dose, rather than a dose based on body size (ie, mg/kg or mg/m²) may be appropriate for ALXN1840.

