# 4.2. Scientific Rationale for Study Design

- This study is being conducted in healthy subjects and not in patients with WD so that the assessments are not confounded by disease activity, comorbidities, or concomitant medications.
- The inclusion and exclusion criteria for this study are consistent with typical Phase 1 clinical pharmacology studies for assessing impact of ethnicity on the medication of interest to minimize assignment bias.
- A two-period, parallel-group study design was adopted to control the variability within and between subjects.
- The washout time between the 2 ALXN1840 dosing periods will be at least 14 days, based on the estimated mean half-life for ALXN1840 of approximately 2 days previously reported in the bioavailability Studies WTX101-101 and WTX101-102, where healthy subjects took oral dose at 60 mg. Therefore, the 14-day washout time between the Period 1 and Period 2 doses is considered sufficient to eliminate, on average, approximately more than 99.2% of the plasma total Mo before the next dose is administered. The 14-day washout time after Period 2 dosing will also ensure that more than 99.2% of ALXN1840 has been eliminated at the subject's EOS visit.

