### 4.3. Justification for Dose

This study is being conducted to support enrollment of Japanese patients with WD into the ongoing Phase 3 Study WTX101-301, which is evaluating ALXN1840 dose titration range from 15 mg once every other day to 60 mg daily. These doses have been studied in previously reported single dose (60 mg in healthy subjects; Studies WTX101-101 and WTX101-102) and multiple dose (15 to 60 mg daily in patients with WD; Study WTX101-201) clinical studies.

ALXN1840 at 60 mg single dose has been shown to be safe and well-tolerated in healthy male and female subjects in Phase 1 bioavailability Studies WTX101-101 and WTX101-102. The 15 to 60 mg/day dose range has also been demonstrated to be efficacious with favorable safety profile in treating patients with WD in the Phase 2 Study WTX101-201 (Weiss, 2017).

The selection of the 15 mg and 60 mg single doses proposed in this study are, therefore, rational and appropriate for this study.

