#### 4.13.2 CL/F and Body Size

Relationships between CL/F and body size (body weight [kg] and BMI [ $kg/m^2$ ]) will be evaluated graphically for the Japanese and non-Japanese cohorts and with combined cohort data. If suggested by the graphs, regression models may be fit to the data

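### Does SAP 4.12.2 need to define the dose behind CL/F and Vd/F, given that 60 mg does not reproduce protocol Tables 3 and 4?

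*SAP*

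**What the plan says.** SAP section 4.12.2 takes as its input "Individual plasma concentration data for ALXN1840, assessed as plasma total Mo concentration-time data". From these it derives CL/F, described as "Apparent total clearance", with the formula "Calculated as $\text{dose}/\text{AUC" (to infinity). Vd/F is dose over the product of λz and the same AUC∞. Neither formula qualifies dose.

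The text around them does give a reading. SAP section 3.1 lists 15 mg and 60 mg of ALXN1840 as the planned doses. In section 4.12.2 the normalised Cmax and AUC values are per mg, and relative bioavailability is reported "by dose strength of 15 mg or 60 mg".

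Protocol section 2.2 (Tables 3 and 4) gives total-molybdenum AUC∞, λz, CL/F and Vz/F from Studies WTX101-101 and WTX101-102. Both used 60 mg: protocol section 4.3 has "single dose (60 mg in healthy subjects; Studies WTX101-101 and WTX101-102" and section 4.2 has "where healthy subjects took oral dose at 60 mg". The tables do not state a dose basis either. Protocol section 9.4.3.1 leaves PK detail to a PK/PD data analysis plan.

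**The concern.** The measured analyte is molybdenum and the administered mass is ALXN1840, of which molybdenum is only a part. Apparent clearance can be expressed against either mass, and the two results differ by a constant. Tables 3 and 4 suggest that the earlier studies did not divide 60 mg by AUC∞. If this study's analysts enter 15 and 60 mg, their CL/F and Vd/F will sit on a scale several times higher than the background values.

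The same parameter is also carried forward. The protocol reports from the earlier studies that "There were no apparent relationships between clearance/bioavailability (CL/F) and body size", and SAP section 4.13.2 plans the same look here: "Relationships between CL/F and body size". A reader who set the two sets of clearances side by side could take a change of units for a real difference between studies.

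**Working it through.** **Inputs.** Mean AUC∞, λz, CL/F and Vz/F come from protocol Tables 3 and 4. The dose is 60 mg, from protocol sections 2.2, 4.2 and 4.3. As 1 ng/mL is 1 µg/L, CL/F in L/h is 60,000 µg divided by AUC∞ in h·ng/mL.

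**Step 1: apply the SAP's CL/F formula with 60 mg.** For the EC tablet fasted column, the formulation type and feeding state of this study, 60,000/17,258 = 3.48 L/h against 0.92 reported.

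| Column | Mean AUC∞ | 60 mg / AUC∞ (L/h) | Reported CL/F | Factor | Reported CL/F × AUC∞ (mg) |
|---|---|---|---|---|---|
| UC fasted (101) | 16,435 | 3.65 | 1.01 | 3.6 | 16.60 |
| UC + PPI fasted (101) | 19,862 | 3.02 | 0.72 | 4.2 | 14.30 |
| UC + PPI fed (101) | 15,603 | 3.85 | 0.94 | 4.1 | 14.67 |
| EC fasted (102) | 17,258 | 3.48 | 0.92 | 3.8 | 15.88 |
| EC fed (102) | 6,973 | 8.60 | 6.34 | 1.4 | 44.21 |
| UC + PPI fasted (102) | 21,047 | 2.85 | 0.66 | 4.3 | 13.89 |

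**Step 2: can averaging explain it?** The tables report the mean of individual ratios; step 1 uses the ratio of means. The mean of dose/AUC∞ can never be below dose divided by mean AUC∞, so averaging can only push the reported CL/F above the third column. Every reported value is below it. Nor do different subjects explain it: n for AUC∞ and CL/F agrees in every column (17, 18, 18 in Table 3; 18, 15, 17 in Table 4).

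**Step 3: bound the dose that was used.** By the same inequality, mean CL/F × mean AUC∞ (last column) is an upper limit on the dose term, with no distributional assumption. Allowing 0.005 L/h for rounding:

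- EC fasted alone: 0.925 × 17.258 = 15.96 mg, so the scale factor against 60 mg is at least 60/15.96 = 3.76.
- One basis in all columns: the tightest limit is UC + PPI fasted (102), 0.665 × 21.047 = 14.00 mg, so the factor is at least 60/14.00 = 4.29.

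**Step 4: Vd/F.** Dividing the 60 mg clearances by mean λz gives about 197 to 271 L in the five columns other than EC fed, against 45.2 to 75.0 L reported, a factor of 3.5 to 4.3. This is supporting evidence only, because the strict inequality does not carry over to a product of two means.

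**Step 5: what a constant factor changes here.** Multiply both doses by any constant k.

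- Cmax, AUCt, AUC∞ and t1/2 = ln(2)/λz contain no dose, so they are unchanged.
- CL/F and Vd/F become k times as large in both cohorts and both periods. Their cohort ratios and %CVs are unchanged.
- Relative bioavailability is a ratio of geometric means at one dose level, so k cancels.
- In the power model, log(k × dose) = log(k) + log(dose). The intercept moves and the slope does not. If the response is dose-normalised, subtracting log(k) from it again leaves the slope alone.
- In plots of CL/F against weight or BMI, the vertical axis is relabelled and the shape and correlation are unchanged.

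**The case for a change.** The best argument for a change is that it is cheap and the discrepancy is real. Steps 1 to 3 use only the documents' own figures and exclude 60 mg as the dose term in the earlier tables. A programmer following the SAP would enter 15 and 60 mg, and the resulting clearances would not be on the scale that the protocol shows as background. SAP section 4.12 carries the title of a PK data analysis plan and gives the formulas, so a definition would belong there. A check of the earlier reports would also show whether Tables 3 and 4 themselves contain an error.

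The arithmetic stands in full. The need for a change does not follow from it.

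- The SAP is not open to two equally natural readings. Its planned doses, per-mg normalisation and dose strengths all mean ALXN1840. With that reading CL/F is exactly the reciprocal of dose-normalised AUC∞, so the list is coherent.
- Neither document plans a numerical comparison with Tables 3 and 4. The body-size finding from the earlier studies concerns absence of a relationship, which does not depend on scale.
- The feared misreading has a ready check. This study also gives 60 mg as EC tablets after a fast, so AUC∞, Cmax and half-life can be set directly against the EC fasted column. If those agreed and CL/F differed several-fold, a scaling difference would be the evident explanation.
- The fuller remedy needs reports outside these documents. If it moved CL/F and Vd/F to another basis, dose would have two meanings in one list and the reciprocal relation would be lost.

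A label giving the unit of dose on the CL/F and Vd/F tables would be a courtesy to readers. It would not change any analysis.

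**Conclusion.** The observation is correct, but it gives no reason to amend the plan. The SAP leaves a small gap in wording that an analyst would fill from context with mg of ALXN1840, and that choice is internally consistent. What fails to match is background from two other studies, by a factor of 3.6 to 4.3 in five columns and 1.4 in the highly variable EC fed column. The basis used there is not stated; that it was the molybdenum content of the dose would be an inference, and nothing here depends on it.

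The effect on this trial's endpoints and conclusions is nil. Only the absolute scale of dose-dependent descriptive quantities is at issue, and CL/F and Vd/F can be rescaled by a constant after analysis if a comparison is ever wanted. This rests on two conditions: that the earlier studies gave 60 mg, as the protocol says, and that the same dose basis is used for both cohorts and both dose levels here, which the SAP's single formula implies.
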